Over the past several years, there were studies suggesting that, compared to the traditionally high frequency stimulation of 130Hz, low frequency stimulation of 60Hz improves the FOG¹⁶⁻¹⁹ and dysarthria^{15, 19}. The beneficial effect was not necessarily only seen in chronically stimulated patients with disease progression, as it was also seen in patients with newly activated bilateral STN DBS¹⁹.

More recently, we for the first time further studied the effect of the 60Hz stimulation on another axial symptom, dysphagia, in patients on bilateral STN DBS who had medication refractory FOG at 130Hz²⁰ (supported by MJFF under Rapid Response Innovation Award program to TX). We found that 60Hz stimulation, compared to the traditional 130Hz, decreased not only the aspiration frequency by modified barium swallowing (MBS) test and swallowing difficulty by swallowing questionnaire, but also the medication refractory FOG (by SWS stand-walk-sit test and FOG questionnaire), and axial symptom subscore and general parkinsonism motor symptom UPDRS-III score²⁰. The beneficial effect of the 60Hz stimulation persisted during the 6-week study period, except that one of the patients had to switch back to 130Hz stimulation in 3 weeks due to worsening of the hand tremor.

The effect of the 60Hz stimulation on STN DBS patients without FOG at 130Hz stimulation was also studied, with significant improvement on axial and motor symptoms in 14 patients in an acute phase study²¹, and mild improvement on gait without improvement on other motor symptoms in another study²², suggesting the overall benefit of the 60Hz stimulation, though may not as great as seen in these with FOG at 130Hz stimulation.

However, it remains unknown whether the beneficial effect of the 60Hz stimulation would persist on extended chronic stimulation beyond the 6-week period, and whether there is carry-over effect during the study across different test conditions of 30-minute apart in our previous study²⁰. Clarifying these two questions is crucial for the clinical application of the 60Hz stimulation chronically and confidently to treat the medication refractory axial symptoms.

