So far, there was only one study showing persistent benefit of the 60Hz stimulation on FOG in 85% of the 13 patients with bilateral STN DBS at medication off state following up in 8 months¹⁶. There were two other studies challenging the chronic benefit of the low frequency stimulation²³⁻²⁴. One of them reported an improvement in the gait immediately after switching the 130Hz stimulation to 80Hz at medication on state in 11 STN DBS patents, but the benefit only lasted for less than 1 month²³. The other one reported no benefit at 80Hz stimulation compared to 130Hz in axial symptoms following for almost 4 months (111.5 days on average) in 45 patients²⁴. Worth noting that none of these two studies was really studying FOG, as one of them had no FOG on exam and the other one was not assessing FOG. Besides, these two studies used 80Hz, instead 60Hz, stimulation. None of them studied swallowing function either.

According to our continuous observation since we published our study²⁰, all of our 5 out of 7 patients who was on 60Hz simulation for 6-week study period remains on 60Hz since then for

its benefit on axial symptoms including FOG, over the period of up to 14 months follow up so far, which indicates a sustained chronic benefits. The 2 of the 7 patients were not on 60Hz stimulation after the previous study because of slightly worsening of tremor in 1 of them, and skin infection after the battery replacement (unrelated to the study) in another one. A formal randomized double blind prospective cross-over study on the chronic benefit of the 60Hz stimulation over an extended period of at least 6 months, corrected for the potential carry-over effects on this crossover study (DBS off, 60Hz or 130Hz while all at medication on state) at the acute (visit 1) and chronic phase (visit 2), is needed to enhance the quality of the study, the evidence level and the level of the recommendation in clinical applications to treat the axial symptoms which are refractory to usual DBS setting and medications with high morbidity and mortality of the PD.

All Parkinson's disease patients who have had aspiration pneumonia within the past one month before the test will be excluded.

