This study is basically an extension study of our previous one (IRB 13-0566; Effects of the stimulation frequency of STN DBS on swallowing function in patients with Parkinson's disease, with publication in reference 20) but with a longer follow-up period (at least 6 months) in more patients and a full evaluation in each visit of maximum 2 visits in some patients.

Hypothesis:

The 60Hz stimulation would have persistent benefit in reducing the aspiration, FOG, other axial and motor symptoms in PD patients with bilateral STN DBS and medication refractory FOG at 130Hz stimulation over an extended period of at least months, even corrected for the potential carry-over effects between different test conditions.

Innovation:

This would be the first study on the chronic effect of the 60Hz stimulation on the dysphagia, FOG and other axial and motor symptoms in PD with bilateral STN DBS with medication refractory FOG at 130Hz stimulation.

Significance:

This study will provide a high evidence level and clinical recommendation on the chronic effect of the 60Hz stimulation on the treatment of the axial symptoms, particularly dysphagia and FOG, which are refractory to usual DBS setting and medications and associated with high morbidity and mortality in PD.

Aims:

Aim 1a: A study on the chronic effect (at least 6 months) of 60Hz stimulation on axial symptoms, including swallowing function and FOG, and parkinsonism to see whether the beneficial effect of 60Hz stimulation compared to 130Hz as revealed in our previous study²⁰, could be sustained in PD patients with bilateral STN DBS with medication refractory FOG at 130Hz.

Aim 1b: This study would also clarify the potential carry-over effect on stimulation (DBS 60Hz, DBS 130Hz, and DBS off, 30 min apart) on acute and chronic phase of the study to

enhance the quality of the study, and the level of evidence and recommendation in clinical applications.

Approach:

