Towards that aim, we will add 12 patients with medication refractory FOG at 130Hz of bilateral STN stimulation at medication on state for two visits of at least 6-months apart. We will plan to have 14 patients enrolled for visit 1, as 2 of them might drop off (or being unable to be on 60Hz due to worsening tremor) before visit 2 (estimated based on our previous study that 1 out of 7 patients could not be on 60Hz due to worsening tremor²⁰). The previous 6 study patients remaining on 60Hz stimulation after the completion of our previous study will be assessed again at visit 2 at least 12 months after the initial visit 1 once we get the IRB approval here.

We will then combine the data from these 14 newly added patients with the previous 7 patients at visit 1 to make 21 patients to complete the visit 1, and 18-20 (12 to 14 newly added patients plus previous 6) patients to complete a longer interval visit 2 of at least 6 months apart.

As our previous study²⁰, it will still be a randomized double-blind prospective cross-over study with medication on state but with 6-8 patients on each group of starting condition (60Hz vs 130Hz vs DBS off, 30 min apart) to allow us analyze the chronic effect and potential carry-over effect of stimulation between different conditions to increase the level of evidence, with 80% power to detect at least 25% difference at two-tail α level of 0.05, as estimated before²⁰. Aspiration frequency on MBS, difficulty in swallowing on questionnaire, FOG in SWS test and questionnaire, and axial subscore and UPDRS-III score will all be assessed accordingly under each DBS conditions as we did in our previous study²⁰, at both visit 1 and visit 2 of at least 6 months apart. The study will be finished in 2 years.

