Specifically, all the study patients will sign a written consent after the IEB approval. The study will be conducted at the Parkinson's Disease and Movement Disorder Center of Department of Neurology, Department of Radiology, Speech and Swallowing Section of Department of Surgery, and Center for Research Informatics at the University of Chicago from August 15, 2015 to March 15, 2017. Advanced PD patients with bilateral STN DBS placement and medication-refractory FOG at routinely used 130-Hz stimulation will be enrolled. The demographics of patients, such as gender, age at the study, disease duration, duration on bilateral STN DBS, and their Parkinson medications, electrode position and active contact positions and settings will all be recorded.

During visit, each patient will receive 3 routine modified barium swallow (MBS) studies in a single day under 3 different DBS frequency conditions (bilateral DBS 130 Hz, DBS 60 Hz, or DBS off) with their usual DBS voltage, pulse width, contact setting, and parkinsonian medication-on state regardless of the study stimulation frequency used. The study will be performed in a randomized and double-blind manner. The order of the DBS conditions will be assigned by the neurologist who will randomly pick up one of the 3 folded sheets with different conditions written on them and program the DBS accordingly, but will not be allowed to participate in any rating or evaluation. Neither the patients, nor the clinical rater, the pathologists for speech and swallowing, or the radiologist is aware of the DBS stimulation frequency condition. A single certified rater will rate all of the clinical scales and questionnaires, and a single swallowing team will conduct all MBS studies and the Penetration-

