Analysis: Changes in measurements between the 60Hz and 130Hz will be analyzed using paired t-test, with swallowing function (objective MBS study and subjective swallowing questionnaire) and FOG (objective SWS study and subjective questionnaire) as primary outcomes, and the rest (UPDRS-III score, axial subscore and tremor subscore) as the secondary outcomes in both acute visit1 and chronic visit 2 phase. Changes between other clinically relevant DBS conditions, including 60Hz vs DBS off, 130Hz vs DBS off, and 60Hz vs 60Hz follow-up (for >8 months on average) will also be explored and similarly analyzed with Bonferroni correction. A two-tailed alpha level of 0.05 will be taken as statistically significant for the comparisons.

Foreseeable difficulty or complications:

We don't anticipate any difficulty in conducting this study, as we had a successful similar study before²⁰, with IRB approval (University of Chicago). Medication refractory tremor could offset the 60Hz use as the tremor could be worse compared to 130Hz. However, most of the patient with axial symptoms has less tremor, and medication refractory tremor is even less. In the past, we had only 1 out of 7 patients who could not be on 60Hz stimulation due to the worsening of the tremor²⁰. No complication of aspiration pneumonia was found or reported before. The DBS condition used in the study will be the routine range of condition used in daily living without side effects. There is no alternative ways to conduct current study in order to get the important questions answered.

Pregnant woman, children or mentally retarded patients: None of them will be involved, as these advanced patients are all at the post-menopausal age. No children will be involved in

these advanced PD patient population. No mental retarded patient will be involved. All the patients will have the capacity to consent.

All study subjects will be paid \$200 for their participation in each visit study.

Research Environments:

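### Aim 1b and the Hypothesis promise a carry-over result and a carry-over-corrected 60Hz effect, but the planned paired t-tests can deliver neither

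*Combined protocol and SAP*

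**What the plan says.** The text before the Hypothesis gives two questions that the study must clarify. One is "whether there is carry-over effect during the study across different test conditions of 30-minute apart". It then calls for a trial "corrected for the potential carry-over effects on this crossover study", in both the acute phase (visit 1) and the chronic phase (visit 2). The Hypothesis states that the 60Hz benefit persists "even corrected for the potential carry-over effects between different test conditions". The Aims section adds: "Aim 1b: This study would also clarify the potential carry-over effect on stimulation".

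The Approach section sets 6 to 8 patients per starting condition "to allow us analyze the chronic effect and potential carry-over effect of stimulation between different conditions", but gives no method. On ordering, it says that the programming neurologist will "randomly pick up one of the 3 folded sheets with different conditions written on them". It does not say whether a sheet fixes the whole order or only one condition, and it describes no balancing.

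The Analysis section states: "Changes in measurements between the 60Hz and 130Hz will be analyzed using paired t-test". The contrasts with DBS off, and 60Hz against 60Hz at follow-up, are handled in the same way with a Bonferroni correction. It mentions no period, sequence, starting-group or preceding-condition term, no carry-over test and no adjusted estimate.

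**The concern.** A paired t-test reduces each patient to one difference between two conditions. The position of each condition in the day, and the condition before it, are discarded. So the planned analysis cannot estimate carry-over or correct for it.

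Aim 1b would have no result, and the clause on correction in the Hypothesis would have no analysis behind it. The protocol rests part of its claim to a higher level of evidence on this correction. With no method fixed in advance, a corrected effect could be claimed from any comparison chosen after the data are seen.

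A second gap appears at visit 2. Newly enrolled patients arrive after at least 6 months on one continued condition. For the earlier cohort the Approach says: "The previous 6 study patients remaining on 60Hz stimulation after the completion of our previous study will be assessed again at visit 2". Nothing says how the frequency on which a patient arrives is to be handled.

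**Working it through.** **Inputs.** From the Approach section: 21 patients at visit 1 and 18 to 20 at visit 2, three conditions per visit, 80% power for a 25% difference at two-sided 0.05. From the Analysis section: paired t-tests. The documents give no carry-over size and no SD, so carry-over sizes below are assumed.

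**1. The plan's own figure.** The 80% power cannot be reproduced or refuted without an SD. It would need an SD of the paired difference of about 35.7% of the 130Hz mean at N=18, or 38.9% at N=21. Below, 80% paired power is taken as the starting point.

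**2. Can carry-over be estimated?** Take N=18 and a linear model with patient, period, condition and preceding condition (none in period 1). Columns: 18 + 2 + 2 + 2 = 24. The rank is 24 with all six orders and also with three cyclic orders. Residual df: 54 - 24 = 30, that is 2N - 6. So the design can support the analysis.

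**3. What the paired contrast estimates.** Let τ be a condition's effect and λ its carry-over into the next period. With six balanced orders each condition comes first in 2 of 6 orders and follows each of the other two in 2 of 6. Therefore:

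- mean at 60Hz = τ60 + (λ130 + λoff)/3
- mean at 130Hz = τ130 + (λ60 + λoff)/3
- difference = (τ60 - τ130) - (λ60 - λ130)/3

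| Assumed λ60 - λ130, as % of true difference | -30 | -10 | 0 | +10 | +30 |
|---|---|---|---|---|---|
| Paired contrast recovers | 110% | 103% | 100% | 97% | 90% |

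With only three cyclic orders the bias changes form. For 60-130-off and its rotations it is -(2/3)(λ60 - λoff). For 60-off-130 and its rotations it is +(2/3)(λ130 - λoff). Carry-over from DBS off then matters too, and equal carry-over from 60Hz and 130Hz no longer ensures an unbiased contrast.

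In a simulation (N=18, 4,000 runs) with no true difference and an assumed 60Hz carry-over of 0.5 SD of the paired difference, the paired test rejected in 8.8% (six orders), 24.5% (first cyclic set) and 5.8% (opposite cyclic set), against a nominal 5%.

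**4. Precision of the adjusted 60Hz-130Hz contrast.** At N=18, 80% paired power on 17 df needs noncentrality 2.973. Adjusted power is the two-sided t power on 30 df at 2.973/√(variance ratio).

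| Orders | Variance relative to paired | Noncentrality | Adjusted power |
|---|---|---|---|
| Six, balanced | 1.25 | 2.66 | 73% |
| Six, free random choice (median; 5th-95th percentile 1.19-2.00) | 1.40 | 2.51 | 68% |
| Three cyclic | 5.0 | 1.33 | 25% |

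**5. Precision of carry-over itself (60Hz against 130Hz as predecessor, six balanced orders).** The variance is 2.25 times the paired variance, so the SE is 1.5 times. The 95% half-width is 2.042 × 1.5 / 2.973 = 1.03 times the difference detectable with 80% power. For a carry-over of 30% of that difference the noncentrality is 0.3 × 2.973 / 1.5 = 0.59, and power is about 9%. Reaching 80% power needs a carry-over of about 1.46 times the detectable difference.

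**6. Arrival frequency at visit 2.** If all patients arrive on the same frequency, an arrival term is identical to the period 1 indicator: 25 columns, rank still 24. It cannot be separated from period.

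**The case against.** The strongest case for leaving the plan alone has four parts.

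- **The Approach section signals the intention.** It forms starting groups for this purpose. That is true, but it is a design feature and a purpose. It names no comparison, model or estimate.
- **Random order and at least 30 minutes on each condition deal with carry-over.** Balanced ordering removes equal carry-over, not unequal carry-over (step 3). Whether 30 minutes is enough is the question the protocol sets itself, so it cannot be assumed.
- **The harm to the main contrast is small and the remedy is weak.** This largely stands. With six balanced orders the distortion is modest, the paired test stays primary, and the carry-over estimate will be imprecise. The modest figure depends on balanced orders, though, which the plan does not promise. The severity comes from the unsupported promise, not from demonstrated bias.
- **The precision figures are idealised.** This also stands. Neither 20 nor 21 divides by six, and the earlier 7 patients' visit 1 orders are already fixed, so 1.25 is a close guide rather than exact. The ratios assume independent errors of equal variance and a carry-over that does not depend on the current condition. They do not transfer directly to a count model for aspiration.

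**Conclusion.** The plan is wrong as written on this point and must be fixed. One of its two stated aims, and the correction claimed in the Hypothesis, have no specified analysis. This follows from the text alone and needs no assumption about how large carry-over is.

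The effect on the main contrast is conditional. It is within ±10% of the true effect for carry-over differences up to ±30% with six balanced orders. It can be larger with cyclic orders, and the direction is unknown in advance. The planned test cannot show which case applies. The unstated ordering also decides whether an adjusted estimate would be useful: 73% power with six balanced orders against 25% with three cyclic ones, given 80% for the paired test.

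**What to change.** Keep the paired comparison as primary and add the following to the plan.

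1. For each visit, a mixed model with random patient and fixed condition, period (1 to 3) and preceding test condition, with period 1 coded as having none. Specify a suitable form for aspiration counts.
2. Report the adjusted 60Hz-130Hz contrast beside the paired one. Report the carry-over estimates, including 60Hz against 130Hz as predecessor, with 95% confidence intervals as the Aim 1b result. State that a non-significant carry-over test does not show that carry-over is absent.
3. Take test orders from a prepared blocked list of all six, for newly enrolled patients at visit 1 and for everyone attending visit 2. Unrestricted random allocation would put 6 to 8 patients in every starting group with a chance of only about 24% at N=21, 22% at N=20 and 4% at N=18.
4. At visit 2, record the frequency on which each patient arrives. State that, where it is the same for all, it cannot be separated from period.
5. Report the earlier 7 patients' visit 1 orders. If they were not recorded, leave those patients out of the visit 1 carry-over model only, and keep them in the paired comparison.

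If this is not added, withdraw Aim 1b and the wording that claims correction for carry-over.

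**Cost.** Plan wording, one order list and one recorded item, with no extra visits or patients. The adjusted contrast has about 73% power where the paired test has 80% (71% if tested on N - 1 df). If the earlier 7 must be left out at visit 1 (14 instead of 21), adjusted power falls to 52-56%, and the carry-over half-width rises to 1.23-1.37 times the detectable difference. The adjusted result should therefore be labelled supportive.

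### Four primary outcomes are compared at two visits at two-sided 0.05, with no lead visit, no success rule and no correction that clearly covers them

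*Combined protocol and SAP*

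**What the plan says.** The only description of the tests is the Analysis paragraph of the combined protocol and SAP. It sets a paired t-test of 60Hz against 130Hz, "with swallowing function (objective MBS study and subjective swallowing questionnaire) and FOG (objective SWS study and subjective questionnaire) as primary outcomes". The remaining scales are placed "as the secondary outcomes in both acute visit1 and chronic visit 2 phase". The Approach section confirms that all the measures are taken at both visits.

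The next sentence turns to other contrasts (60Hz vs off, 130Hz vs off, 60Hz vs 60Hz at follow-up), which "will also be explored and similarly analyzed with Bonferroni correction". The paragraph ends: "A two-tailed alpha level of 0.05 will be taken as statistically significant for the comparisons".

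Three other places bear on this point:

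- Aim 1a asks whether the earlier benefit is sustained over at least 6 months.
- The Approach section claims "80% power to detect at least 25% difference at two-tail α level of 0.05", relying on an estimate from the previous study, and plans to "combine the data from these 14 newly added patients with the previous 7 patients at visit 1 to make 21 patients".
- The Approach section identifies the modified barium swallow (MBS) measure as aspiration frequency. For the stand-walk-sit (SWS) test it lists two measures, freezing spells and completion time, and does not say which is primary.

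**The concern.** Four primary outcomes at two visits give eight primary tests, each apparently judged at 0.05. Nothing says whether success means one outcome, some or all, or whether visit 1, visit 2 or both must show it. The choice could therefore be made after the results are known.

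The risk is greatest at visit 1. A significant acute result there could be reported as primary success although the stated aim is chronic. Visit 1 is also the weaker basis for a new claim, because 7 of its 21 patients come from the earlier study, whose favourable result the background already reports: "We found that 60Hz stimulation, compared to the traditional 130Hz, decreased not only the aspiration frequency by modified barium swallowing (MBS) test". The plan says the study will give a high level of evidence and support a clinical recommendation, and an undeclared success rule undercuts that.

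**Working it through.** **Inputs.** From Analysis: two-sided 0.05, paired t-tests, four primary outcomes, two visits. From Approach: 21 patients at visit 1 and 18–20 at visit 2 (12 to 14 new plus 6 earlier). The background gives a lower count of earlier patients still on 60Hz ("all of our 5 out of 7 patients who was on 60Hz simulation for 6-week study period remains on 60Hz since then"), so 12 + 5 = 17 is included as a lower bound. The documents give no correlation between outcomes or visits. I assume 0 to 0.8 and show 0.9 as a sensitivity case.

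**The plan's own figure.** The 80% power cannot be reproduced, because no outcome or standard deviation (SD) is given. Working backwards, 80% power at 0.05 needs a standardized paired effect of 0.701 with n=18 or 0.660 with n=20. A 25% difference then implies an SD of the paired difference of 25/0.701 = 35.7% or 25/0.660 = 37.9% of the 130Hz mean. Nothing in the documents allows this to be checked.

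**Independent tests, no true effect.** The chance of at least one significant result among k tests is 1 − 0.95^k.

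- k=4: 1 − 0.8145 = 18.5%.
- k=8: 1 − 0.6634 = 33.7%.
- If both SWS measures counted, k=5 gives 22.6% and k=10 gives 40.1%.

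**Correlated tests, no true effect.** These are simulated paired t-tests with equal correlations, 21 patients at visit 1, and the visit-2 patients (17, 18 or 20) a subset of them. There were 100,000 runs per setting, and significance was counted in either direction.

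| Rule for success | Corr. 0 | 0.5 | 0.8 | 0.9 |
|---|---|---|---|---|
| Any of four at visit 2 | 18.5% | 16% | 12% | 10% |
| Any of eight | 34% | 26% | 17–18% | 12–14% |
| All four at visit 2 | below 0.01% | 0.1% | 1.0% | 1.7% |

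The eight-test row is approximate, because it treats all 21 visit-1 patients as new data.

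**Results favouring 60Hz only.** With independent tests, 1 − 0.975^4 = 9.6% and 1 − 0.975^8 = 18.3%. At correlation 0.8 these fall to about 6% and 8–9%. The nominal rate is 2.5%.

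**All four must succeed.** The last row of the table is not this rule's error rate, because it assumes that no outcome responds. With three real effects and one null outcome (n=18), false success is about 4–5% at a standardized effect of 1.0 and about 5% at 1.5. The rule is controlled at 5%.

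**Any one outcome significant in the same direction at both visits.** Suppose the acute effect is real (standardized effect 1.0) and the chronic effect is nil. The visit-1 condition is then nearly always met, so the rule reduces to any of four favourable results at visit 2. Simulation gives about 6–10% for correlations of 0.8 to 0, so this rule is not controlled at 5%.

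**The case against.** **Bonferroni may already cover the primary tests.** The phrase "will also be explored and similarly analyzed with Bonferroni correction" could mean that the primary tests were corrected too, and a correction over all of them would hold the error at or below 5%. This cannot be excluded. However, the phrase sits in the sentence on other contrasts, and no family size is given. The threshold could be 0.05/4 = 0.0125, 0.05/8 = 0.00625 or something else.

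**Aim 1a makes visit 2 primary.** It points that way, but the Analysis paragraph gives the two visits equal standing. Naming visit 2 alone would still leave any-of-four uncontrolled.

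**The percentages depend on assumptions.** This stands. They require every null to be true and an assumed correlation, and they count results in favour of 130Hz as well. At correlation 0.9, or counting only benefit from 60Hz, they are smaller, though still above nominal.

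**Three stronger readings the documents do not support.** A reader might infer:

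- that the trial has a 34% false-positive rate. That holds only for independent tests under an any-of-eight rule, which the plan does not adopt. An all-four rule fits the text equally well and is controlled.
- that the MBS measure is also open, since both penetration and aspiration are scored. Approach names aspiration frequency, so only the SWS measure is undetermined.
- that the 80% power is known to ignore multiplicity. Its basis lies in a cited source and cannot be seen.

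**Conclusion.** The concern holds as an undeclared success rule, not as a fixed error rate. The plan as written allows primary success to be claimed on any one of the four visit-2 tests or any one of all eight, and neither rule is controlled at 5%. The sizes are about 19% down to 12% for the former and about 34% down to 17% for the latter. These figures assume no true effect, either direction and correlations of 0 to 0.8. Requiring one outcome to succeed at both visits does not cure this if only the acute effect is real.

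This should be corrected. The gap affects how a positive result may be claimed, not whether the study can be run.

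**What to change.** Before results are seen, add to the Analysis paragraph:

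*The primary analysis is 60Hz vs 130Hz at visit 2. The four primary outcomes are aspiration frequency on MBS, the swallowing questionnaire, one named SWS measure and the FOG questionnaire, tested by Holm at familywise two-sided 0.05. Visit-1 tests and the other SWS measure are secondary.*

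A fixed sequence or an all-four rule, each test at 0.05, is also acceptable if declared in advance. If sustained benefit is meant to require both visits, add a same-direction visit-1 requirement to the visit-2 Holm test, which can only lower the error. State which contrasts Bonferroni covers and over how many tests. State the outcome, SD and alpha behind the 80% power, and whether it allows for multiplicity.

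The change is wording only and needs no new data, but it costs power:

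- **Holm.** An effect with 80% power at 0.05 has about 58% at the strictest step (0.0125) with n=17–20. Restoring 80% there would need about a 31% difference in place of 25% (25 × 0.868/0.701 = 31.0 at n=18), or 25–29 patients at visit 2. If all four effects are real at the size that has 80% power at 0.05, power per outcome averages 67–71% and at least one is declared with probability 77–97%, for correlations of 0.8 to 0.
- **Fixed sequence.** The first outcome keeps 80%. The second has 64–73%, the third 51–68% and the fourth 41–65%; the lower ends are 0.8², 0.8³ and 0.8⁴.
- **All four.** Success has 41–65% probability on the same assumption.
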